6.5.2 Concomitant Medications

Concomitant medications taken from the start of dosing (Dosing Visit 1) through the 1-Month Post-treatment Follow-up Visit will be recorded in the CRF. For medications associated with the management of angioedema attacks, study personnel will record the start and stop dates, dose, unit, frequency, route of administration, and indication in the subject's CRF. For medications not associated with the management of HAE, study personnel will record the start and stop dates (if known), route of administration, and indication for which the medication was administered in the subject's CRF.

6.5.3 Prohibited Medications

Use of C1 INH therapy (other than study drug) for the prevention of angioedema attacks is prohibited during the study. Details on the management of breakthrough angioedema attacks are discussed in Section 6.12.

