The burden of HAE on patients and family members is considerable with respect to its detrimental effects on physical health, career and work productivity (missed days), education (missed days), and mental health (feelings of panic and anxiety) (Aygören-Pürsün et al. 2012; Caballero et al. 2014; Lumry et al. 2010). Individual patients may be debilitated by their symptoms for up to 100 days per year, making employment or education difficult (Nzeako et al. 2001). Because of its unpredictability, HAE can be life-altering regardless of angioedema attack frequency. Patients live in constant fear of the next attack, and often arrange their lives around these events. Some patients who have had laryngeal attacks, or who have had family members die due to laryngeal attacks, never leave their local environment for fear of being distant from the safety of their home and the physicians who know and understand their illness (Levi et al. 2006).

The only product approved in Japan for the management of patients with HAE is Berinert P, a human C1 inactivator indicated to treat acute attacks of HAE. There is no approved therapy in Japan for long-term C1 INH protein replacement or prevention of angioedema attacks in patients with HAE. Given the questionable safety and efficacy of unapproved therapies currently being used to prevent angioedema attacks in Japan (ie. danazol, tranexamic acid), an unmet medical need exists for a subset of Japanese patients who experience frequent or life-threatening attacks and are not adequately managed with repeated acute treatments. CINRYZE is the only C1 INH protein replacement therapy in the world that is approved for both long-term (routine) prevention of angioedema attacks and treatment of acute attacks in patients with HAE. Routine replacement of C1 INH in patients who experience frequent attacks, severe attacks, and/or larvngeal attacks has been associated with improved patient outcomes, including a reduction in potential mortality, number of hospitalizations, and increased quality of life (eg, relief from anxiety, flexibility to travel, freedom to pursue educational and professional goals) (Craig et al. 2009; Kalfus et al. 2012; Gower et al. 2012). Consequently, international consensus guidelines have endorsed longterm replacement of C1 INH in the appropriate patient populations (Cicardi et al. 2012; Bowen 2011; Bowen et al. 2010).

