4.2 Exclusion Criteria

To be eligible for this protocol, a subject must not:

- 1. Have a history of hypercoagulability (abnormal blood clotting).
- 2. Have a diagnosis of acquired angioedema or be known to have C1 INH antibodies.
- 3. Have a history of allergic reaction to C1 INH products, including CINRYZE (or any of the components of CINRYZE) or other blood products.
- 4. Have received C1 INH therapy or any blood products within 3 days before the first dose of study drug.
- 5. Have had signs or symptoms of an angioedema attack within 2 days before the first dose of study drug.
- 6. Have any change (start, stop, or change in dose) in androgen therapy (eg, danazol, oxandrolone, stanozolol, testosterone), tranexamic acid, epsilon-aminocaproic acid (EACA), or other antifibrinolytics within 14 days before the first dose of study drug.
- 7. If female, have started taking or changed the dose of any hormonal contraceptive regimen or hormone replacement therapy (eg, estrogen/progestin containing products) within 2 months before the first dose of study drug.
- 8. Be pregnant or breastfeeding.
- 9. Have received an investigational drug other than those required for prevention or treatment of angioedema attacks within 30 days before the first dose of study drug.
- 10. Have, as determined by the Investigator and/or the Sponsor's Medical Monitor, any surgical or medical condition that could interfere with the administration of study drug or interpretation of study results.

Protocol 0624-209 with Amendments 1, 2, 3, 4, and 5 CINRYZE (C1 inhibitor [human])

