6.10 Restrictions

Subjects should maintain their normal diets, medications, and activities of daily living. During the study, subjects will be asked to avoid known triggers of angioedema attacks to the best of their ability (eg, foods, activities, medical procedures, environments). To the extent possible, subjects should postpone elective procedures (eg, dental work) while participating in the study. If a procedure cannot be postponed, the subject or parent/guardian will notify the Investigator and the information will be recorded in the CRF.

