#### 5.7.4. SENSITIVITY ANALYSIS

The following sensitivity analyses will be performed for efficacy analysis on NNA described in Section 5.7.1.

The first sensitivity analysis includes only subjects with treatment compliance. The definition of treatment compliance will be given in Section 5.8.8. That is, only subjects who have no dose interruption and receive 24 complete infusions are included in the analysis.

In the second sensitivity analysis, all FAS subjects will be included in this sensitivity analysis, however data will only include up to the point when non-treatment compliance occurred.

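### Other HAE prophylaxis added or raised after dose 1 is discouraged but not prohibited, and no attack-rate analysis responds to it, so its effect would be read as CINRYZE effect

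*Protocol*

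**What the plan says.** The only listed prohibition during the study is in Protocol 6.5.3: "Use of C1 INH therapy (other than study drug) for the" prevention of attacks. Androgens, tranexamic acid and other antifibrinolytics are not named there.

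These drugs do appear at entry. Exclusion 6 in Protocol 4.2 opens "Have any change (start, stop, or change in dose) in androgen therapy" and ends with "antifibrinolytics within 14 days before the first dose of study drug". After dose 1 the relevant sentence is in 6.10: "Subjects should maintain their normal diets, medications, and activities of daily living". The protocol's introduction shows that the issue is live in this population, referring to "unapproved therapies currently being used to prevent angioedema attacks in Japan (ie. danazol, tranexamic acid").

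SAP 5.7.1 compares on-treatment NNA with NNA over the 3 months before dosing and counts subjects with reductions of at least 50%, 70% and 90%. SAP 5.7.4 has two sensitivity analyses. The first keeps only subjects compliant with CINRYZE; in the second, "data will only include up to the point when non-treatment compliance occurred". SAP 5.8.8 defines compliance by CINRYZE infusions and the gaps between them. SAP 5.8.7 tabulates long-term prevention drugs but does not link them to NNA. The rescue-medication rule in SAP 5.7.1 picks up acute-treatment indications only.

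On triggers, Protocol 6.10 says: "During the study, subjects will be asked to avoid known triggers of angioedema attacks to the best of their ability". Inclusion 7 asks for the same agreement. Nothing comparable is requested or recorded for the 3 historical months.

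**The concern.** NNA is an uncontrolled before-after contrast. Whatever changes at study start or during the 12 weeks, and affects attacks, moves the apparent reduction. A new or increased androgen or antifibrinolytic is such a change, and the protocol itself regards it as important enough to exclude a subject when it happens in the 14 days before dose 1. Once dosing has begun, the same change is only discouraged and has no consequence in the analysis.

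At stake is how the NNA reduction and the responder counts are read. A subject insufficiently controlled on CINRYZE who is given another prophylactic would contribute the combined effect of both drugs, and could be counted as a responder to CINRYZE. With as few as 6 completers, one such subject is visible in the headline percentages.

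**Working it through.** **No plan figure to reproduce.** Protocol 7.1 gives a minimum of 6 completers without an effect size, variance or power, and Protocol 7.3 makes the analysis descriptive. The checks below show how an added treatment passes into NNA.

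**Inputs from the documents.** On-treatment NNA = attacks ÷ days × 30.4; historical NNA = attacks in 3 months ÷ 3 (SAP 5.7.1). There are 24 doses at an average spacing of 3.5 days (SAP 5.8.8), so the period is about 23 × 3.5 + 1 = 81.5 days. The overseas placebo-controlled prevention study had 6.3 against 12.8 attacks per 12 weeks (Protocol 1.1.2), a reduction of 1 − 6.3/12.8 = 50.8%.

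**Assumed inputs.** The effect and start day of the other prophylactic, and the subject's attack rates. The documents give none of these, so ranges are shown.

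**1. Co-intervention acting throughout treatment but not before it.** With CINRYZE effect r and other effect c, the apparent reduction is 1 − (1 − r)(1 − c).
- r = 0: the apparent reduction equals c.
- r = 50.8%: c = 10%, 30% or 50% gives 55.7%, 65.5% or 75.4%.

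**2. Add-on begun during treatment.** Assume 3.0 attacks/month historically and 2.0 on CINRYZE alone (1 − 2.0/3.0 = 33%, not a responder). An add-on with effect a starts on day d. In expected rates the factor 30.4 cancels:

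NNA = [2.0·d + 2.0(1 − a)(81.5 − d)] ÷ 81.5

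| Add-on effect a | NNA, d = 28 | Reduction | NNA, d = 42 | Reduction |
|---|---|---|---|---|
| 30% | 130.9/81.5 = 1.61 | 46% | 139.3/81.5 = 1.71 | 43% |
| 50% | 109.5/81.5 = 1.34 | 55% | 123.5/81.5 = 1.52 | 49.5% |
| 75% | 82.75/81.5 = 1.02 | 66% | 103.75/81.5 = 1.27 | 58% |

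**3. When the 50% responder status flips.** NNA must fall to 1.5 or below, so 2.0·a·(81.5 − d)/81.5 must be at least 0.5.
- d = 28: a ≥ 0.25 × 81.5/53.5 = 38%.
- d = 42: a ≥ 0.25 × 81.5/39.5 = 52%.

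One subject in 6 is 1/6 = 17 percentage points.

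**4. Prophylaxis begun before dose 1.** Take the historical window as 3 × 30.4 = 91.2 days, c = 30% and no CINRYZE effect. If the drug starts s days before dose 1, the historical rate relative to no prophylaxis is [(91.2 − s) + 0.7s]/91.2, and the on-treatment rate is 0.7.
- s = 15: 1 − 0.7/0.951 = 26.4% spurious reduction.
- s = 45: 1 − 0.7/0.852 = 17.8%.
- s = 91.2 (unchanged through the whole window): 1 − 0.7/0.7 = 0%.

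A start within the window but before the 14-day limit therefore passes through in part, while stable use cancels.

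**The case against.** **The plan is not silent.** Section 6.10 points towards stable medication. On-study prophylaxis will be tabulated (SAP 5.8.7), and subject-level medication and attack listings are planned (SAP 9.1.3). With a handful of subjects, a reader could find an add-on by eye. That is fair, and it limits the harm. But the listings do not say what the NNA or responder status would have been without the add-on. The disallowed-medications deviation category (SAP 5.4) need not capture a drug that 6.5.3 does not disallow.

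**The size depends on assumptions.** This stands. A 30% add-on effect does not flip the example subject at either start day, and 50% does so only from day 28. Nor do the documents say how often subjects with continuing attacks would be given another prophylactic; their stated routes are supplemental CINRYZE (Protocol 6.12.1) and discontinuation for lack of efficacy (Protocol 6.15.1).

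A reader might infer four stronger points that the documents do not support:
- *Any prophylaxis carried into the study inflates the result.* Step 4 shows that unchanged use cancels. Therapy stopped or reduced during the window would bias against CINRYZE.
- *Exclusion 9 opens the same gap*, because it exempts HAE drugs from the rule on receiving "an investigational drug other than those required for prevention or treatment of angioedema attacks within 30 days before the first dose". That rule concerns receipt before dosing. Use continued unchanged across both periods cancels, and use ended at entry works against CINRYZE.
- *Exclusion 6 and 6.5.3 contradict each other.* One is an entry rule, the other an on-study prohibition that does not name a drug class; 6.10 agrees with the former. There is no conflict to reconcile.
- *Triggered attacks should be removed from both periods.* Triggers would come from 3-month recall at baseline and from a daily diary on study. Suppose there is no drug effect and no avoidance, 20–40% of attacks are triggered, recall identifies 50–80% of those and the diary all of them (all assumed). The remaining rate then falls spuriously by 1 − (1 − 0.2)/(1 − 0.2 × 0.8) = 5% up to 1 − (1 − 0.4)/(1 − 0.4 × 0.5) = 25%.

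**Conclusion.** The point holds for prophylaxis started or raised after dose 1: it is discouraged, not prohibited, and no NNA, responder or sensitivity analysis responds to it. Any benefit would be counted as CINRYZE effect. In the example, a true 33% reduction appears as 43% to 66% across the assumed add-on effects and start days.

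Nothing in the documents shows that any subject added prophylaxis, so it would be wrong to conclude that the observed reduction is inflated. The analysis is descriptive: interpretation is affected, not a type I error rate. The example also works in expected rates, whereas real attack counts are whole numbers.

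Trigger avoidance is a separate and weaker matter. The protocol requests it only for the study period, to the best of the subject's ability, and some subjects may already have been avoiding their triggers. In a single-arm before-after design its effect cannot be separated from that of the drug. It is a limitation to state, not one that an analysis can remove.

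**What to change.** Add one paragraph to SAP 5.7.4: repeat the NNA and 50/70/90% responder analyses with both attacks and days counted only up to the first on-study start or dose change of any non-study long-term HAE prophylaxis. Protocol 6.5.2 already has dates, dose and indication recorded for such medication, so no new data are needed. If no subject changed therapy, say so; the result then stands more firmly.

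In the same output, flag subjects who started, stopped or changed such therapy within the 3-month historical window. Protocol 6.5.1 collects HAE therapy for the 12 months before Day 1 with indication and, if known, start and stop dates. It does not list dose, so earlier dose changes can be flagged only where the CRF captured them.

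State in the SAP and the report that trigger avoidance was requested only on study and cannot be distinguished from drug effect.

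The cost is small: some programming, and shorter follow-up for affected subjects in that analysis. If an add-on was prompted by a run of attacks, stopping there may also overstate the earlier rate, so the result should be read beside the main analysis and not replace it. No change to clinical rules is proposed.

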6.6 Nonpharmacologic Treatments and Procedures

Nonpharmacologic treatments received from the Screening Visit through the 1-Week Post-treatment Follow-up Visit will be recorded in the CRF. To the extent possible, procedures (eg, surgical, diagnostic, or dental) should be avoided during study participation (see Section 6.10); however, those occurring through the 1-Week Post-treatment Follow-up Visit will be recorded in the CRF.

6.7 Clinical Laboratory Parameters

Subjects will have blood samples collected for routine clinical laboratory testing at the time points specified in Schedule 1 and Schedule 3. Testing will be performed at a central laboratory. The following clinical laboratory parameters will be analyzed:

Protocol 0624-209 with Amendments 1, 2, 3, CINRYZE (C1 inhibitor [human])

- Hematology: CBC consisting of WBC and differential counts and percentages, RBC count, hemoglobin, hematocrit, and platelet count.
- Coagulation: PT, aPTT, INR.
- Clinical Chemistry: BUN, creatinine, glucose, sodium, potassium, chloride, CO₂, AST, ALT, alkaline phosphatase (ALP), CPK, total bilirubin, calcium, phosphorus, total protein, and albumin.
- Virology: HIV (single assay antibody/Western Blot) and hepatitis (Hepatitis B Surface Antigen, Hepatitis C Antibody).
- Urinalysis with microscopy: pH, specific gravity, dipstick (protein, glucose, ketones, hemoglobin), and microscopic evaluation (RBCs, WBCs, crystals, casts, bacteria).

For all females of childbearing potential, pregnancy testing (in accordance with standards at the site) will be performed at the time points specified in Schedule 1 and Schedule 3.

Additional clinical laboratory testing may be performed during the study if clinically indicated, and may be completed locally or sent to the central laboratory. Site staff will manually enter local laboratory results into the CRF.

6.8 Sample Collection for Pharmacokinetic, Pharmacodynamic, and C1 INH Antibody Analyses

Subjects will have blood samples collected for the determination of plasma concentrations of C1 INH antigen (protein volume), functional C1 INH activity (potency), complement C4, and C1q at the time points specified in Schedule 4. In addition, blood samples will be collected at Visits 1 (baseline), 8, 16, and 24 and 1 month (30 ± 2 days) after the last dose of study drug for C1 INH antibody analyses (see Schedule 1 and Schedule 3).

The actual date and time of each sample collection will be recorded. Plasma samples for the determination of C1 INH antigen (protein volume), functional C1 INH activity (potency), complement C4, and C1q concentrations and C1 INH antibodies will be analyzed using fully validated methodology. Details on the processing of blood samples for PK/PD and immunogenicity assessments will be provided in a separate study manual.

NOTE: If a subject presents to the site with a breakthrough angioedema attack, every effort should be made to obtain a PK blood sample before treatment. In addition, if the subject receives CINRYZE for treatment of the attack, every effort should be made to obtain a 1-hour post-treatment sample; if a second dose of CINRYZE is administered, an additional 1-hour post-treatment sample should be obtained if possible. These samples will be collected as an unscheduled visit and analyzed for C1 INH antigen (protein volume) and functional C1 INH activity (potency). Additional blood samples for PK/PD and C1 INH antibody assessments may be collected during the study if clinically indicated.

Selected samples may be analyzed to investigate incurred sample reproducibility (ISR) of the bioanalytical methods and/or incurred sample stability (ISS). These analyses are only to investigate the reproducibility of the bioanalytical methods used to determine concentrations of

C1 INH antigen (protein volume) and functional C1 INH activity (potency) in study samples and/or to investigate the stability of the incurred samples. All ISR and ISS results collected will be reported in a separate table in the bioanalytical report. All samples will be disposed of at the conclusion of the study. Details of disposal will be documented and maintained with the study file at the analytical laboratory.

Selected samples may be retained to investigate immunogenicity to C1 INH.

6.9 Total Blood Volume Collected

During the study, subjects who weigh 25 kg or more will have approximately 220 mL of blood collected for clinical safety laboratory testing (hematology, chemistry, coagulation, and virology), PK/PD assessments, and immunogenicity (C1 INH antibody) testing (exclusive of unscheduled visits). Subjects who weigh less than 25 kg will have approximately 140 mL of blood collected (exclusive of unscheduled visits). In addition, for subjects who weigh less than 25 kg, the Screening Visit must occur at least 14 days before Dosing Visit 1.

6.10 Restrictions

Subjects should maintain their normal diets, medications, and activities of daily living. During the study, subjects will be asked to avoid known triggers of angioedema attacks to the best of their ability (eg, foods, activities, medical procedures, environments). To the extent possible, subjects should postpone elective procedures (eg, dental work) while participating in the study. If a procedure cannot be postponed, the subject or parent/guardian will notify the Investigator and the information will be recorded in the CRF.

6.11 Study Diary

Beginning at Dosing Visit 1, subjects (or their caregivers such as a parent or guardian, based on the ability of a child) will use a study diary each day to document specific information about any angioedema attack symptoms that occur (eg, including the location, severity, pain score, and duration of symptoms) and details on the self-administration of investigational product. At the first dosing visit (Dosing Visit 1), study personnel will instruct each subject (or caregiver) how to complete the study diary.

Study personnel will review the diary for completeness and accuracy at each scheduled dosing visit. The Investigator or designee will use subject-reported diary data as reference information, in addition to any other available medical records, to record and evaluate events related to breakthrough angioedema attacks in the CRF.

6.12 Angioedema Attacks

An angioedema attack will be defined as any subject-reported (or caregiver-reported) indication of swelling or pain at any location following a report of no swelling or pain on the previous day (ie, there must be a full symptom-free calendar day preceding the onset of symptoms for an attack to be considered a new attack). Therefore,

- Attacks that progress from 1 site to another will be considered a single attack;
- Attacks that begin to regress and then worsen before complete resolution will be considered 1 attack; and
- Attacks that begin, appear to resolve, and then reappear without a symptom-free calendar day reported after the appearance of resolution will be considered 1 attack.

NOTE: An angioedema attack does NOT include swelling due to trauma or arthritis, or symmetrical non-painful swelling of the lower extremities.

In this study, angioedema attacks will not be reported as adverse events unless the attack meets the definition of a serious adverse event (see Section 9.1.4).

6.12.1 Treatment of Breakthrough Angioedema Attacks

A breakthrough attack is defined as an angioedema attack that occurs during long-term prevention therapy with CINRYZE. If a subject receives CINRYZE for treatment of a breakthrough angioedema attack, they should continue their protocol-defined treatment schedule without alteration regardless of when the supplemental dose is administered.

If a breakthrough angioedema attack occurs during the 12-week treatment period through 1-week post-treatment, a supplemental dose of CINRYZE may be administered by IV infusion for treatment of the attack either by the Investigator (or qualified delegate) or subject (or caregiver) if trained and deemed independent to self-administer (1000 U for subjects ≥6 years of age or 500 U for subjects 2-5 years of age). If the subject does not adequately respond to the initial dose within 1 hour, a second dose of CINRYZE may be administered (1000 U for subjects ≥6 years of age or 500 U for subjects 2-5 years of age).

It is recommended that treatment of breakthrough attacks occurs at the investigational site whenever possible so that clinical assessments can be completed as specified. It is preferred that subjects receive CINRYZE within 4 hours but not more than 8 hours after the onset of breakthrough attack symptoms if treatment can occur at the investigational site.

Subjects (at least 12 years of age or their caregivers) who have completed the required self-administration training and deemed independent (per criteria specified in Section 5.3.1) may elect to self-administer CINRYZE for a breakthrough attack. Note: Subjects (or caregivers) who are participating in self-administration training and not yet qualified as independent cannot self-administer CINRYZE for a breakthrough attack; rather they must seek treatment at the investigational site. If a subject (or caregiver) who self-administers CINRYZE for treatment of a breakthrough attack does not respond adequately after instructed treatment (ie, 2 doses separated by 1 hour), they should notify the Investigator and seek medical attention or report to study site to seek further treatment and relief of symptoms.

In addition to the administration of CINRYZE, subjects are allowed to receive symptomatic treatment for breakthrough angioedema attacks (eg, IV fluids). The administration of narcotics and antiemetics is discouraged during the 4-hour post-infusion assessment period to allow for evaluation of the response to CINRYZE. Other treatments for angioedema attacks (eg, another C1

INH product such as Berinert P, tranexamic acid, fresh frozen plasma) are not permitted at the investigational site unless a subject does not adequately respond following treatment with CINRYZE (ie, 2 doses separated by 1 hour).

